**Table 3 Objectives and Endpoints (cont.)**

Objectives	Endpoints
Exploratory	

 
Assess the durability of the effect of RG7774 on DR.
 
	
 
Proportion of participants with either a stable (<math>\pm 1</math> step change), worsened (<math>>1</math> step increase) or improved (<math>>1</math> step decrease) DRSS between Week 36 and Week 48.
 

 
Assess the efficacy of RG7774 on visual acuity and anatomical outcome measures using spectral domain optical coherence tomography (SD-OCT) among eyes with DME at baseline.
 
	
 
Change from baseline in participants with DME at baseline in:               
 
BCVA (as measured on the ETDRS chart at a starting distance of 4 meters) at post-baseline visits.
 
Central subfield thickness on SD-OCT over time at post-baseline visits.
 
 
 
Proportion of participants with absence of signs of DME and normalized Central Subfield Thickness (CST) at post-baseline visits.
 

 
Assess the effect of RG7774 on visual function.
 
	
 
Change from baseline in Contrast Sensitivity at post-baseline visits in the study eye (Pelli-Robson, qCSF) or in both eyes (qCSF).
 
Change from baseline in low luminance visual acuity (LLVA) at Week 36 visit in the study eye.
 

 
Assess the effect of RG7774 on visual fields.
 
	
 
Change from baseline in mean threshold at post-baseline visits.
 
Change from baseline in point-by-point Standard Automated Perimetry at post-baseline visits.
 

 
Assess systemic pharmacokinetics and exposure-response/safety relationships of RG7774 (and its metabolite[s] as appropriate).
 
	
 
PK parameters of RG7774 (and its metabolite[s] as appropriate) in plasma and (if applicable) in optional aqueous humor.
 

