### 9.4.2 Efficacy Analyses

For the primary and exploratory efficacy analyses, see [Table 7](#).

All efficacy data will be summarized by randomized treatment group and visit for the ITT population.

Participants in whom any of the events (i) to (iii) described in Section 6.5.3 occur in either eye, or participants who require rescue treatment prior to the week 36 assessment will still be considered as completing participants and will enter the analysis as non-responders at the visit at which the event occurs as well as all subsequent visits.

The primary endpoint will be analyzed using GEE with a binomial distribution using a logit link function for odds ratios and unstructured covariance. In case of convergence issues, an alternative covariance structure will be used. The model will include categorical covariates for treatment group, visit, and visit by treatment group interaction term. Also the baseline stratification factors will be added. Least squares means on the probability scale for each treatment group with the corresponding 90% confidence intervals and odds ratios relative to the placebo group will be computed for each visit. Full details of the statistical analysis will be described in a separate document prior to any unmasking of the study.

In accordance with the ITT principle, assessments at all visits will be included in the analysis. This includes any assessments made at visits while the participant is on randomized study treatment as well as any assessments made at visits after randomized study treatment has been terminated.

If visits occur as described in Section 1.3, a response assessment at week 36 will be available for all participants. Despite best efforts, there may be missing response assessments at week 36 (e.g., for participants withdrawing consent or being lost to follow-up). *The statistical methodology to deal with missing data will be described in a separate technical document prior to any unmasking of the study.*

The proposed methodology is known to render unbiased effect estimates only under the restrictive missing completely at random assumption (Liang and Zeger, 1986). Therefore, if the amount of total missing data (across patients and visits) exceeds 10% of all expected data, sensitivity *analyses* will be carried out (Molenbergs and Verbeke, 2005).

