**Table 7 Efficacy Statistical Analysis Methods**

Endpoints	Statistical Analysis Methods

Primary
 
Proportion of participants with <math>\geq 2</math> step improvement in ETDRS DRSS from baseline at Week 36 measured in the study eye.
	
Generalized Estimating Equations (GEE) with a binomial distribution taking into account repeated measures within each participant.

Secondary
 
Incidence of ASNV, new PDR, new DME, and pre-existing DME requiring intervention.
 
Change from baseline in BCVA at Week 36 in the study eye.
	
Descriptive summaries of the number, frequency and percentage of participants experiencing the types of events.
 
Analysis of variance model for longitudinal data taking into account repeated measures within each participant

Exploratory
 
Proportion of participants with <math>\geq 2</math> step worsening in ETDRS DRSS from baseline at Week 36 measured in the study eye.
	
GEE with a binomial distribution taking into account repeated measures within each participant.

Proportion of participants with <math>\geq 3</math> step improvement in ETDRS DRSS from baseline measured in both eyes at post-baseline visits.
	
Analysis performed in subgroup of ITT population with bilateral disease. Modeling will be similar as for the primary endpoint.

Proportion of participants with <math>\geq 3</math> step worsening in ETDRS DRSS from baseline measured in both eyes at post-baseline visits.
	
Analysis performed in subgroup of ITT population with bilateral disease. Modeling will be similar as for the primary endpoint.

Proportion of participants with either a stable (<math>\pm 1</math> step change), worsened (<math>>1</math> step increase) or improved (<math><1</math> step decrease) DRSS between week 36 and week 48.
	
Modeling will be similar as for the primary endpoint.

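### Table 7 reverses the inequality that defines off-treatment DRSS improvement, so decreases of two or more steps fall in no category

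*Combined protocol and SAP*

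**What the plan says.** Table 3 (Objectives and Endpoints) lists durability of effect as an exploratory objective. Its endpoint has three categories of DRSS change over the off-treatment period. *Stable* is a change within one step either way, *worsened* is an increase of more than one step, and the third category reads "improved ( >1 step decrease) DRSS between Week 36 and Week 48".

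Table 7 (Efficacy Statistical Analysis Methods) repeats the endpoint. *Stable* is unchanged and the next category again reads "worsened ( >1 step increase", but the third now reads "improved ( <1 step decrease) DRSS between week 36 and week 48", so that a less-than-one sign stands before "step decrease) DRSS between week 36 and week 48" where Table 3 has a greater-than-one sign.

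The method given for that row is one line: "Modeling will be similar as for the primary endpoint". The primary model is in section 9.4.2: "The primary endpoint will be analyzed using GEE with a binomial distribution using a logit link function for odds ratios and unstructured covariance". On its terms the same section says: "The model will include categorical covariates for treatment group, visit, and visit by treatment group interaction term". The stratification factors are added to these.

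Section 9.4.2 points to Table 7 for the primary and exploratory efficacy analyses. It leaves the complete analysis specification to a further document, to be written before unmasking.

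**The concern.** Two current tables define the same category with opposite inequalities, and the incoherent one is in the analysis section. Section 4.2.3 explains why the endpoint exists: earlier trials suggest that DRSS gains may be lost after treatment stops. The table therefore has to separate participants who keep improving from those who hold steady and those who slip back. A category that nobody can enter, together with a group that has no category, defeats that purpose.

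The method line adds a smaller difficulty. The primary model is built for a yes/no response seen at several visits, whereas this endpoint is one change per participant sorted into three groups. The row does not say which group counts as the event.

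**Working it through.** The plan states no figure for this endpoint, so there is none to reproduce. Its power range of 74% to 88% (section 9.2) belongs to the primary comparison and does not use this definition.

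**Step 1: classify every change.** Let *d* be the change in DRSS steps from Week 36 to Week 48, with positive values meaning worse. The inputs are the definitions in Tables 3 and 7.

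- Stable, both tables: |*d*| ≤ 1
- Worsened, both tables: *d* > 1
- Improved, Table 3: −*d* > 1
- Improved, Table 7 as printed: 0 < −*d* < 1 (a decrease, and smaller than one step)

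| *d* | Table 3 | Table 7 as printed |
|---|---|---|
| −4, −3, −2 | improved | no category |
| −1, 0, +1 | stable | stable |
| +2, +3, +4 | worsened | worsened |

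Under Table 3 each whole-step change falls in exactly one category. Under Table 7 no whole number satisfies 0 < −*d* < 1, so *improved* is empty and every change of −2 or lower is left out.

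**Step 2: effect on the reported proportions.** If *k* of *n* participants in an arm have a decrease of two or more steps, Table 7 gives *improved* = 0/*n* instead of *k*/*n*. The three proportions then add up to (*n* − *k*)/*n*. With the 40 completers per arm of section 9.2, each such participant accounts for 1/40 = 2.5 percentage points. The documents give no expected value for *k*.

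**Step 3: can the primary model's terms be fitted?** With one record per participant, the visit column equals the intercept and the visit-by-treatment columns equal the treatment columns. The intercept, two treatment indicators, visit and two interaction columns make 6 columns, but the rank is 3. The visit and interaction terms are not estimable.

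**Step 4: what remains once they are dropped.** One category was coded 0/1 and fitted with treatment only, on illustrative simulated data with 40 participants per arm. The binomial GEE and ordinary logistic regression gave identical coefficients: −1.386, 0.767 and 0.655. A usable binary analysis therefore exists. The row simply does not state it.

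**The case against.** The strongest reply is that this is a typographical slip, perhaps a lost minus sign from a condition such as *d* < −1, which would agree with Table 3. Section 3 names Table 3 as the place where endpoints are defined, and the symmetric wording of the other two categories makes the intent plain. That is probably right. It shows what the correction should be, but Table 7 is still wrong as printed. Because the point rests on one character, the sign should be confirmed on the issued page.

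A reader might also infer that participants with no change land in two classes. The documents do not support this, because the category is a decrease and zero is not one. Overlap appears only if the condition is stretched to −*d* < 1. Changes of 0 and +1 would then be both stable and improved, and changes of +2 or more both worsened and improved. Nothing in the text invites that reading. Decreases of two or more steps are unclassified even then.

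A second tempting inference is that the assigned model makes the row impossible to run. This too goes further than the text. The row asks for similar modelling, not identical modelling, and the endpoint wording allows three separate yes/no indicators. Details are also deferred to a later document. This part of the objection stands, so the model line is under-specified rather than wrong. The deferral does not cure the threshold, because the later document would inherit two conflicting definitions.

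**Conclusion.** Table 7's threshold for *improved* is wrong as written and conflicts with Table 3. Followed literally, it gives an empty category and leaves every decrease of two or more steps unclassified, so the durability proportions would be wrong. This assumes that DRSS change is counted in whole steps and that the printed sign is as read.

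The practical size depends on how many participants improve further after treatment stops, which the documents do not estimate. It may be few, given the plan's own expectation that gains may fade.

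The consequence is confined to one exploratory endpoint. The primary analysis, its power and the sample size do not depend on it. The method line needs clarification only.

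**What to change.** In Table 7, change the *improved* condition to a decrease of more than one step, matching Table 3.

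In the method cell of the same row, state that each of the three categories is analysed as a yes/no indicator with treatment group and the stratification factors and without visit terms. Alternatively, state that the three proportions are reported by arm with 90% confidence intervals, the level section 9.4.2 already uses. A proportional-odds model is a further option, but nothing in the documents requires it.

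The cost is one symbol and one line of text, with no change to data collection or sample size. Making the change before unmasking keeps the choice of definition and method independent of the results.

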**Table 7 Efficacy Statistical Analysis Methods (cont.)**

Change from baseline in participants with DME at baseline in:
 
 
• BCVA (as measured on the ETDRS chart at a starting distance of 4 meters) at post-baseline visits.
 
• Central subfield thickness on SD-OCT at post-baseline visits.
 
 
Proportion of participants with absence of signs of DME and normalized CST over time
	
Analysis of variance model for longitudinal data taking into account repeated measures within each participant.

Change from baseline in Contrast Sensitivity at post-baseline visits in the study eye (Pelli-Robson, qCSF) or in both eyes (qCSF).
	
Analysis of variance model for longitudinal data taking into account repeated measures within each participant.

Change from baseline in LLVA at Week 36 visit in the study eye.
	
Analysis of variance model for longitudinal data taking into account repeated measures within each participant.

Absolute change from baseline in mean threshold and in point-by-point Standard Automated Perimetry at post-baseline visits.
	
Analysis of variance model for longitudinal data taking into account repeated measures within each participant.

PK parameters of RG7774 (and its metabolite(s) as appropriate) in plasma and (if applicable) in optional aqueous humor.
	
Descriptive summaries of the PK parameters (e.g., <math>C_{max}</math>, AUC, etc.)

Change from baseline in blood levels of HbA1c.
	
Descriptive summaries by treatment group and visit

Performance of the advanced analytic tools
	
Analysis of the exploratory efficacy endpoints

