## **PROTOCOL AMENDMENT, VERSION 5 RATIONALE**

Protocol BP41321 has been amended to optimize enrolment and execution of the study, by modifying some entry criteria and reducing the length of the visits. Changes to the protocol, along with a rationale for each change, are summarized below:

- Section 1.3 (tables 1 and 2) has been modified to reduce the number of assessments and thus the duration of the visits as follows:
  - Removal of patient-reported outcome questionnaires (i.e., the National Eye Institute Visual Functioning Questionnaire-25 [NEI VFQ-25] and the Low Luminance Questionnaire [LLQ])
  - Removal of the optional UWF-FP assessments
  - Visual Field assessment made optional
  - The two post-dose pharmacokinetic (PK) samples have been made optional
  - Perform Pelli-Robson and low luminance visual acuity (LLVA) assessments only in the study eye
  - Additional Pelli-Robson assessment at Week-4 visit
  - Perform LLVA assessment only at visits on Day 1, at Week 36, and in case of early termination
- To reflect the changes in Section 1.3, Table 3 (Section 3 Objectives and Endpoints), Sections 8.1.2.3 (Low-Luminance Visual Acuity), 8.1.2.4 (Contrast Sensitivity), 8.1.2.5 (Visual Fields [Optional]), 8.2.1 (Ocular Examination), and Table 7 (Section 9.4.2 Efficacy Analyses) have been updated; Section 8.1.2.1 (Patient-Reported Outcomes), Appendix 8 (National Eye Institute Visual Functioning Questionnaire - 25 [NEI VFQ-25]), and Appendix 9 (Low Luminance Questionnaire [LLQ]) have been removed.
- Entry criteria (Sections 5.1 and 5.2) have been modified to facilitate enrolment in the trial by:
  - Adding an additional rescreening for inclusion criterion 3
  - Increasing the permitted HbA1c level from 10% to 12% (inclusion criterion 9)
  - Excluding recruitment of participants who had periocular pharmacological intervention (exclusion criterion 1)
  - Allowing recruitment of participants who were enrolled in other previous retinal/ ocular clinical trials, in specific circumstances (exclusion criteria 9 and 10)
  - Allowing enrolment of participants with no active HBV, HCV (exclusion criterion 22 and Appendix 4 Clinical Laboratory Tests)

- Allowing recruitment of participants who had COVID-19 more than 30 days prior to screening (exclusion criterion 24)
  - Allowing the principal investigator decide on abuse of alcohol/ substances considering the results of the test and the medical history of the participant (exclusion criterion 26)

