**Table 1 Schedule of Activities – Main Table (cont.)**

13. *One PK sample to be collected at all visits prior to study treatment administration. At visits Day 1, Day 28, and Day 252 two additional post-dose samples may be collected optionally. The two samples should be obtained at 1-3 hours, and 3-5 hours post-dose, respectively. Timing between the two post-dose samples should be approximately 2 hours.*
14. [REDACTED]
15. *Study eye only.*
16. qCSF to be performed only if the site has the capabilities to perform this assessment.
17. *Optional Visual Field assessments should be performed in study eye only when the site has the capabilities to perform this assessment.*
- 18a. Only one FFA modality will be performed in each patient: *ultra-widfield-FFA* will be performed preferentially, if the site has the capabilities to perform this assessment. If not available, 7F-FFA will be performed.
- 18b. Fluorescein Angiography assessments not to be done more often than every *12 weeks*.
19. Study medication will be administered to participants directly in the study clinic on the day of site visit. The participant has to avoid taking medication before going to the site on the day of site visit.
20. Adverse event collection will be done throughout the full length of the study.
21. Patient Engagement App (PEMA) will be used at discretion of the participant, if applicable, throughout the full length of the study (no time restriction on Day 1).

**Table 2 Schedule of Activities – Reduced Assessments as from the Time of Rescue Treatment and up to and including Week 36**

	Assessments in case of rescue treatment
Previous and Concomitant Treatments / Medications	x
Physical Examination	x
Vital Signs	x
Triplicate ECG-12 lead	x
Hematology	x
Blood Chemistry	x
Coagulation	x
Lipids	x
HbA1c	x
Urinalysis	x
TSH	x
C-SSRS (Form "Since Last Visit")	x
PK Sample	x
IOP	x
BCVA	x
Slit Lamp	x
Indirect Ophthalmoscopy	x
Fundus Photography (7F-FP)	x
SD-OCT	x
Dispensing and/or return of study medication	x
RG7774 / placebo	x
Adverse Events	x
Optional Aqueous Humor sample 	x

Optional aqueous humor sample collection to be performed prior to the intravitreal rescue treatment in participants who give additional consent.

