### **8.10.3 Assessments at Study Treatment Completion / Early Termination Visit**

Participants who complete the 36-week treatment phase will be asked to return to the clinic for two visits with fewer assessments compared to the regular visits:

- A safety follow-up visit, 28 ( $\pm 7$ ) days after the final dose of study treatment (week 40 visit),
- An efficacy visit, 84 ( $\pm 7$ ) days after the final dose of study treatment (week 48 visit).

Participants who discontinue from the study treatment phase early, will have an early termination visit and be asked to return to the clinic 28 ( $\pm 7$ ) days after the final dose of study treatment for a safety follow-up visit.

- if the early termination visit occurs within 14 days of the last site visit, the list of assessments to be performed will be reduced.
- If the early termination visit happens more than 14 days after a site visit a complete set of assessments needs to be performed.

See Section [1.3](#) ([Table 2](#)), and Sections [8.1](#) and [8.2](#) for further details.

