## 9.4 STATISTICAL ANALYSES

### 9.4.1 Demographics and Baseline Characteristics

Demographics, baseline characteristics (including subject disposition and medical history) and all baseline laboratory values will be summarized descriptively by treatment using frequency tables and summary statistics providing means, medians, standard deviations, and extreme values.

**Definition of baseline:** Baseline for all efficacy and safety analyses is defined as the last non-missing value recorded prior to or on the first study drug administration.

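### Table 7 gives LLVA a repeated-measures model, but Version 5 schedules at most one post-baseline LLVA per participant; the row should name a baseline-adjusted Week 36 analysis

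*Combined protocol and SAP*

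**What the plan says.** **Endpoint.** Table 3 lists change from baseline in "low luminance visual acuity (LLVA) at Week 36 visit in" the study eye as an exploratory endpoint. Table 7 repeats it: "Change from baseline in LLVA at" the Week 36 visit.

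**Method.** The method cell for that row in Table 7 reads "Analysis of variance model for longitudinal data taking into account repeated measures within each participant". The same wording serves endpoints measured at several post-baseline visits, such as contrast sensitivity. No covariates are named in the row.

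**Schedule.** The Version 5 amendment rationale says: "Perform LLVA assessment only at visits on Day 1, at Week 36, and in case of early termination". The LLVA row of Table 1 carries three marks to match: Day 1, Week 36, and the early termination column for visits 14 days or more after a site visit.

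**After early termination.** Section 8.10.3 states: "Participants who discontinue from the study treatment phase early, will have an early termination visit". These participants then return for the 28-day safety follow-up, at which Table 1 marks no LLVA.

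**After rescue.** Table 2, headed "Reduced Assessments as from the Time of Rescue Treatment and up to and including Week 36", does not list LLVA. The reduced schedule applies to the study eye when the study eye is the one rescued.

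**Baseline and detail.** Section 9.4.1 says: "Baseline for all efficacy and safety analyses is defined as the last non-missing value recorded prior to or on the first study drug administration". Section 9.4.2 adds: "Full details of the statistical analysis will be described in a separate document prior to any unmasking of the study".

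**The concern.** A repeated-measures model earns its place when each participant contributes several post-baseline values. It estimates how those values correlate, and earlier visits can then inform a missing later one. LLVA under Version 5 offers neither benefit, because nothing is measured between Day 1 and the end of treatment. The row therefore names a method that does not describe what will be done, and it suggests some help with missing Week 36 values that the schedule cannot give.

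The second matter is precision. With one post-baseline value, the Day 1 measurement is the most useful remaining source of information. The row uses it by subtraction and says nothing about using it as a covariate. Section 4.2.5 explains that BCVA is not expected to move much in eyes that already see well, which is why further measures of visual function are explored; LLVA is one of them under Table 3. Precision lost on such a measure is lost for no return.

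**Working it through.** **1. The plan's own figure.** The documents give no SD, power or sample size for LLVA. The only power statement (Section 9.2) concerns the primary endpoint: Fisher's exact test, 40 completers per group, 15% against 40% to 45%, two-sided 0.10, giving 74% to 88%. Full enumeration gives 75.5% and 87.5%, and 40/(1 − 0.10) = 44.4, rounded up to 45 per group. That agrees with the plan, and nothing below bears on it.

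**2. Scheduled post-baseline LLVA values per participant (Version 5).**

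| Course | Scheduled post-baseline LLVA values |
|---|---|
| Completes to Week 36, no study-eye rescue | 1 (Week 36) |
| Full early termination visit | 1 (that visit), none later |
| Study eye rescued, stays to Week 36 | 0 from rescue onward, so none at Week 36 |
| Only the non-study eye rescued | 1 (study eye stays on the full schedule) |

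The maximum is one. BCVA differs: its secondary endpoint is also at Week 36, but Table 1 schedules it at several post-baseline visits, so the longitudinal model fits there.

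**3. What the stated model does with one value.** One data set was simulated with 40 per group, SD 10, correlation 0.7 and one post-baseline value each. Change scores were fitted three ways.

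| Fit | Dose effects against placebo | SE (both) |
|---|---|---|
| One-way ANOVA | 3.3612, 3.2185 | 1.7067 |
| GEE, exchangeable, model-based SE | 3.3612, 3.2185 | 1.7067 |
| GLS | 3.3612, 3.2185 | 1.7067 |

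The fits are identical. The model runs, and it is a one-visit ANOVA of change.

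**4. What a baseline covariate would add.** Let s² be the variance of LLVA, assumed equal at Day 1 and Week 36, and ρ the correlation between the two. The documents give no ρ, so a range is shown.

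- Variance per participant, unadjusted change: 2s²(1 − ρ)
- Variance per participant, ANCOVA: s²(1 − ρ²)
- Ratio, ANCOVA to change: (1 − ρ²)/[2(1 − ρ)] = (1 + ρ)/2

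| Assumed ρ | ANCOVA / change variance | Inverse | SE of change analysis larger by |
|---|---|---|---|
| 0.5 | 0.75 | 1.33 | 15% |
| 0.7 | 0.85 | 1.18 | 8% |
| 0.8 | 0.90 | 1.11 | 5% |
| 0.9 | 0.95 | 1.05 | 3% |

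Adding baseline in the simulated data set (ρ = 0.7) gave SEs of 1.5865 and 1.5824. The squared ratios to 1.7067 are 0.864 and 0.860, close to the theoretical 0.85.

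**The case against.** **Details are deferred.** Section 9.4.2 promises a separate document before unmasking, and Table 7 names no covariates for any continuous endpoint, secondary BCVA included. Baseline adjustment for LLVA may well be intended. This stands: the documents neither state nor exclude it, so the precision figures are conditional on an unadjusted analysis. It does not rescue the method cell, which describes repeated measures that the current schedule does not produce.

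**Table 7 was updated for Version 5.** The amendment rationale lists it among the changed sections, and the LLVA endpoint cell carries the italics that mark new text. A reader might infer that the row was overlooked altogether. It was not; the endpoint cell was revised and the method cell kept its generic wording.

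**Earlier protocol versions.** Participants treated before Version 5 may have had LLVA at more visits. Those schedules are not in the documents, so the count of one is claimed only for participants treated under Version 5.

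**Early termination values.** A reader might infer that these enter the model as a further visit level, which would set different people against each other. No passage says so. Section 9.4.2 includes assessments at all visits in general terms, while Tables 3 and 7 fix the endpoint at Week 36. How an early termination LLVA is to be treated is simply unstated.

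**ANCOVA is not the only valid choice.** True. A model with Day 1 as a response would have two values per participant, but Table 7 makes change from baseline the outcome.

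**Conclusion.** The stated method does not fit the Version 5 LLVA schedule. With at most one post-baseline value per participant, it amounts to a one-visit ANOVA of change scores.

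Two stronger readings are tempting and are not supported. The first is that the row cannot be run: it can, and reducing it to ordinary ANOVA introduces no bias. The second is that the Day 1 value goes unused: it is used by subtraction, and only its use as a covariate is unstated.

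The size is modest. If the analysis is unadjusted, ANCOVA would have 0.75 to 0.95 of its variance for assumed correlations of 0.5 to 0.9, with equal variances at the two visits. If the separate document already adjusts for baseline, the precision point disappears and only the wording and the unstated handling of early termination values remain. Week 36 LLVA will in either case be missing by schedule after study-eye rescue, with no intermediate values to inform it. This is an inexpensive improvement to one exploratory endpoint, not a threat to the trial's validity.

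**What to change.** Change the method cell of the LLVA row in Table 7 to an ANCOVA of Week 36 LLVA, or of its change from baseline, with treatment group, Day 1 LLVA and the three stratification factors. With Day 1 LLVA in the model, either outcome gives the same treatment estimate.

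Add two sentences there or in the separate analysis document:

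- LLVA values from early termination visits are summarised separately and do not stand in for Week 36.
- Table 2 schedules no LLVA after study-eye rescue, so those Week 36 values will be missing; report their number by treatment group.

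If participants treated under earlier versions have additional LLVA visits, say how those are used.

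The cost is one table cell and a few lines of text before unmasking. No visit, measurement or sample size changes.
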